We conducted a single-blind, randomized controlled trial approved by the institutional review board of Shanghai Changhai Hospital (ClinicalTrials.gov. ID: NCT03514966). From May 7 to May 31 2018, consecutive patients (aged \geq 18 years) with upper abdominal complaints requiring MCCG in Changhai Hospital were included after providing informed consent. Patients with the following [7] were excluded: (1) dysphagia or symptoms of gastric outlet obstruction, suspected or known intestinal stenosis, overt gastrointestinal bleeding, history of upper gastrointestinal surgery or abdominal surgery altering gastrointestinal anatomy, or post abdominal radiation; (2) congestive heart failure, renal insufficiency, under therapeutic anticoagulation, in poor general condition (American Society of Anesthesiologists class III/IV), claustrophobia, metallic parts, a pacemaker or other implanted electromedical devices, or artificial heart valves; (3) pregnancy or suspected pregnancy; (4) exclusion criteria for standard magnetic resonance imaging examination such as the presence of surgical metallic devices, even though its low magnetic field technically would not interfere with such devices; or (5) currently participating in another clinical study [6].

Examination were performed by one qualified capsule endoscopist with an experience of more than 500 cases of MCCG operation. Other two endoscopists ([name], [name]) was blinded to the type of gastric preparation, independently graded the quality by reviewing the images captured by MCCG. When discrepancies arise over the grading results, this will be resolved by consensus discussion between the two endoscopists, with arbitration by a third endoscopist ([name]) and made the final decision.

Study intervention

Magnetically controlled capsule gastroscopy system

The MCCG system used in this study includes an endoscopic capsule, a portable external data recorder, a guidance magnet robot, and a computer workstation with software for real-time viewing and controlling, all provided by Ankon Technologies Co. Ltd (Shanghai, China). The endoscopic capsule has a size of 27 * 11.8 mm, with light-emitting diodes surrounding two metal oxide chip cameras placed at both ends. Images are captured and

recorded at a rate of 2 frame/s, and information sent wirelessly to the data recorder. The view angle of capsule is 140°, and view distance is 0 to 30 mm. It is powered by two silver oxide batteries for up to 10-12 hours. In addition, a permanent magnet was also contained within the dome of capsule, which is guided by the C-arm type guidance magnet robot with five degrees of freedom—two rotational degrees and three translational degrees. Through simulation on the basis of the magnetic field generated by the magnet guidance system, the magnetic field can be adjusted and reaches a maximum of 200 mT. Using two joysticks, the examiner can control capsule movement to varying the strength of magnetic field by altering the distance of the magnet from the patient and change the polarity of the magnet. The size of lesions could be measured by the ESNavi software [5, 6].

Gastric preparation regimen and MCCG examination protocol

After overnight fasting (> 8h), subjects receiving magnetically controlled capsule gastroscopy at the institution who met the inclusion criteria will be randomly allocated into 1 of 2 groups (1:1): position change or conventional groups. An independent research assistant generated the computerized random number sequence. The sequence was concealed in an opaque envelope until the intervention was obtained from eligible subjects, study nurses telephoned the independent research assistant, and then informed the patient's intervention allocation. Right after ingesting 5 g dimethicone (Zigong Honghe Pharmaceutical Co.,Ltd; Sichuan, China) mixed with 100 ml of water, subjects in the conventional group were allowed to walk freely; while subjects in the position change group were instructed by the study nurses to repeatedly change the body position according to a pre-specified protocol for a period of 15 min: in the order of supine position, left lateral position, with a duration of 1 min for each position. Thirty and forty min after dimethicone administration, subjects in both groups would additionally take 200 ml and 800 ml water, respectively before undergoing MCCG examination (Supplementary Figure S1).

After attaching the data recorder, patients were asked to lie down on the examination couch beneath the guidance magnet robot. Then the capsule was swallowed in a supine position with approximately 100 ml of water for investigating the esophagus. The patient remained sat upright to facilitate the esophageal passage if capsule stop in the esophagus more than one minute. The examination was conducted with the patient lying in left lateral, supine, and finally right lateral positions. If difficulties in navigation were encountered, further positional change (including the prone position) was tried. Additional water was needed if distension was insufficient. When the capsule reached the stomach, the investigator lifted the capsule away from the posterior wall, rotated and advanced the capsule to the fundus and cardiac regions, and then to the gastric body, angulus, antrum, and pylorus. The gastric examination time of MCCG was recorded. If lesions were identified during MCCG examination, conventional EGD was performed according to standard practice to obtain biopsy or for therapeutic intervention.

Outcome parameters

Primary Outcome Measure

The primary outcome was gastric cleanliness score (GCS). Six primary anatomical landmarks of the stomach (cardia, fundus, body, angulus, antrum, and pylorus) were recorded for evaluation. A 4-point grading scale was introduced to define the cleanliness as excellent (no adherent mucus and foam: score 4), good (mild mucus and foam but does not obscure vision: score 3), fair (considerable amount of mucus or foam present precluding a completely reliable examination: score 2) and poor (large amount of mucus or foam residue needing water to clear it: score 1) (Supplementary Figure S2) [6, 7]. GCS was the total scores of all six landmarks, ranging from 6 (completely unprepared) to 24 (perfect). GCS of \geq 18 was regarded as acceptable.

Secondary Outcome Measure

Secondary outcomes included detection rate of positive findings, number of lesions per patient (NLPP), gastric examination time, and safety of MCCG. Positive findings defined as any pathology detected by MCCG, including polyp, ulcer, gastric fundus varices, submucosal tumor, and carditis. The diffuse lesions such as superficial, atrophic, and erosive gastritis were defined as negative findings [6]. NLPP was defined as the number of positive findings divided by the total number of patients, the location of NLPP were also recorded. Gastric examination time was determined using digital stopwatch in the ESNavi software. Safety of MCCG, or adverse events, defined as symptoms or signs such as abdominal distention, nausea, or vomiting, were monitored closely during the MCCG procedure. Capsule retention (i.e., a capsule endoscope remaining in the gastrointestinal tract for more than two weeks or a capsule endoscope that requires directed intervention or therapy to aid its expulsion) was monitored and followed up for up to two weeks.

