In order to define the sample size, we carried out an exploratory study enrolling 20 patients in each group. Mean gastric cleanliness score in the position change and conventional groups were 20.1 and 19.4, respectively. This study was a superiority study based on two-sided alpha as 0.05 and the power as 80%, thus 64 patients (32 patients in each group) were required by using NCSS-PASS 11 program (version 11.0.7, NCSS, Kaysville, Utah, USA). Considering a withdrawal rate of 20%, we enrolled 80 patients at least. Statistical analysis was performed using SPSS Statistics software version 18.0. Descriptive statistics were given as means ± standard deviation (SD). Differences in categorical variables between patient groups were compared by using the Chi-square test; differences in means were compared with the independent *t*-test. In GCS comparison and subgroup analysis which lack of normal distribution for quantitative data, we used Mann-Whitney test for comparison of the two groups. A *P*-value of < 0.05 was considered to be statistically significant.

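### Does calling a gastric cleanliness total of 18 or more acceptable, with no minimum per landmark, undermine the analysis?

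*Protocol*

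**What the plan says.** The Protocol's Primary Outcome Measure section names the score: "Six primary anatomical landmarks of the stomach (cardia, fundus, body, angulus, antrum, and pylorus) were recorded for evaluation". The two upper grades are "excellent (no adherent mucus and foam: score 4") and "good (mild mucus and foam but does not obscure vision: score 3"). The third is fair, "considerable amount of mucus or foam present precluding a completely reliable examination: score 2", and the lowest is poor, score 1. The section continues "GCS was the total scores of all six landmarks", gives a range of 6 to 24, and closes with the statement that a score of at least "18 was regarded as acceptable".

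The Secondary Outcome Measure section reads: "Secondary outcomes included detection rate of positive findings, number of lesions per patient (NLPP), gastric examination time, and safety of MCCG". A rate of acceptable preparation is not among them.

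The SAP bases the sample size on mean scores from an exploratory study: "Mean gastric cleanliness score in the position change and conventional groups were 20.1 and 19.4, respectively". It assigns the Mann-Whitney test to the GCS comparison and does not mention the 18-point cut-off.

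**The concern.** The Protocol's own wording creates the tension. A landmark graded 2 is one where the examination was not completely reliable, yet a patient can have such landmarks and still be called acceptable. Six landmarks at 3, with nothing obscured, and the pattern 4, 4, 4, 2, 2, 2, with half the landmarks compromised, share the total of 18 and the label. The exploratory means of 19.4 and 20.1 lie in a region where two low landmarks are still possible.

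If the trial rested on this label, the stakes would be real. A difference in acceptable rates might not reflect a difference in how many stomachs were fully visible. A gain in the total also does not show whether position change cleared obscured landmarks or only moved good ones to excellent.

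**Working it through.** **Inputs.** From the Protocol: six landmarks, grades 1 to 4, unweighted sum, cut-off 18. From the SAP: means 20.1 and 19.4, two-sided alpha 0.05, power 80%, 32 per group, 20% withdrawal.

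**1. Range of the score.** 6×1 = 6 and 6×4 = 24, as the Protocol states.

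**2. What a total can hide.** With k landmarks at 2 or less, the largest possible total is 24 − 2k, so k ≤ (24 − total)/2.

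| Total | Most landmarks at 2 or less |
|---|---|
| 18 | 3 |
| 19–20 | 2 |
| 21–22 | 1 |
| 23–24 | 0 |

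For poor landmarks, 24 − 3j ≥ 18 gives j ≤ 2. Enumerating all 4^6 = 4096 patterns confirms these limits. Each extreme at 18 needs all remaining landmarks to be excellent.

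**3. Where the cut-off enters the plan.**

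- Primary outcome: the GCS total. The cut-off is not used.
- Secondary outcomes: positive findings, lesions per patient, examination time, safety. The cut-off is not used.
- Sample size: the difference in means, 20.1 − 19.4 = 0.7, then 64/(1 − 0.20) = 80. The cut-off is not used.
- Named test for GCS: Mann-Whitney. The cut-off is not used.

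Moving the cut-off, removing it or adding a per-landmark condition would leave all four unchanged.

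**4. What the cut-off means.** 18/6 = 3, so it asks for an average grade of good. Any threshold on a sum lets a high item offset a low one. The Protocol applies the threshold to the total, so the label does not claim that each landmark was clear.

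**5. How often it could matter.** The documents give no landmark frequencies, so this step rests on assumptions. Let grades be 2, 3 or 4 only, with the group means at the SAP's values. The mean per landmark is 3 + P(4) − P(2), so P(4) = mean/6 − 3 + P(2). With independent landmarks, SD = √{6[P(4) + P(2) − (P(4) − P(2))²]}. Example for mean 19.4 and P(2) = 0.10: P(4) = 0.333 and SD = √{6[0.433 − 0.054]} = 1.51. Ranges below run over the two means.

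| Share of landmarks fair | Acceptable patients with at least one fair: independent | Same, latent correlation 0.3 | SD, independent |
|---|---|---|---|
| 0 | 0 | 0 | 1.04–1.17 |
| 0.5% | 2–3% | 1% | 1.06–1.19 |
| 2% | 9–10% | 3–5% | 1.15–1.27 |
| 5% | 22–24% | 10–13% | 1.29–1.40 |
| 10% | 41–44% | 23–27% | 1.51–1.60 |
| 20% | 69–71% | 47–51% | 1.86–1.94 |

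The extreme case of three fair landmarks is far rarer. Among acceptable patients it is at most 0.2% when 10% of landmarks are fair. When 20% are fair it is 1.5–3.0% (independent) or 0.6–1.6% (correlation 0.3).

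**6. Which rows fit the SAP.** The SAP states no SD. With 32 per group, the t-test needs a standardised difference of 0.711, so the implied SD is 0.7/0.711 = 0.98; the normal approximation gives 0.7/[(1.960 + 0.842)×√(2/32)] = 1.00. Even with no fair landmarks, the independent model already exceeds this. With correlation 0.3 the model SD is 1.41–1.63 at zero fair and 2.2–2.8 at 10–20% fair. If the implied SD is right, only the top rows of the table come close to it.

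**The case for a change.** The strongest reply is that the Protocol puts the label inside the definition of the primary outcome. Any acceptable rate that is later reported will be read through it, and the SAP's general chi-square rule for categorical variables could be applied to such a rate. The preparation serves visibility, and detection of positive findings is a secondary outcome, so a per-landmark view is clinically natural. The landmark grades are already recorded, and a descriptive row would cost almost nothing. The SAP's undefined subgroup analysis cannot be assumed to supply it.

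Most of this stands as fact. The label does allow low landmarks, neither document plans a landmark-level summary, and a higher total alone does not show which landmarks improved. What does not follow is that the plan is wrong. The harm needs a proportion that the documents do not plan to report, read as a claim that they do not make. A stricter rule has its own cost: one fair landmark in an otherwise perfect stomach (2 + 5×4 = 22) would fail a requirement that every landmark reach 3, which is why such a rule would not be a clear replacement for the total.

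**Conclusion.** The concern does not hold. The limits of three fair or two poor landmarks at a total of 18 are exact, but the cut-off determines no listed outcome, no named test and no part of the sample size. Following the plan as written gives no wrong result on this account, and the effect on estimates, type I error, power and N is nil. A supplementary table by landmark would be a reporting preference.

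This rests on the outcome lists and analysis text as they stand. If the acceptable rate were made an endpoint, the question would have to be reopened. The frequency of hidden low landmarks is unknown. The percentages above are model assumptions that give grade 1 no probability, and the SD of about 0.98 used to judge them is inferred from the sample size and not stated in the SAP.

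### The adverse-event definition has no pre-preparation reading and no new-or-worse rule, so it does not prevent presenting symptoms and intended water distension from being counted as harms of MCCG

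*Protocol*

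**What the plan says.** Under Secondary Outcome Measure, the Protocol lists safety as a secondary outcome: "Safety of MCCG, or adverse events, defined as symptoms or signs such as abdominal distention, nausea, or vomiting". The same sentence sets the window: these symptoms "were monitored closely during the MCCG procedure". It has no new-onset or worsening criterion, severity grade or attribution rule. Capsule retention, by contrast, has its own definition and follow-up of up to two weeks.

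The opening paragraph of the Protocol describes the population: consecutive adults "with upper abdominal complaints requiring MCCG in Changhai Hospital were included". It excludes patients with "dysphagia or symptoms of gastric outlet obstruction, suspected or known intestinal stenosis", but not those with ordinary bloating or nausea. No baseline symptom assessment is described anywhere.

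The section on the preparation regimen and examination gives both arms 100 ml of water with the dimethicone. Then "subjects in both groups would additionally take 200 ml and 800 ml water, respectively before undergoing MCCG examination", and about 100 ml more goes down with the capsule. During the examination, "Additional water was needed if distension was insufficient".

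The SAP has a general chi-square test for categorical variables and nothing specific to adverse events.

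**The concern.** The definition turns on whether a symptom is present during the examination, not on whether it changed. Two sources of background can enter.

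- **Presenting symptoms.** A patient who arrives nauseated and is no different during the examination meets the definition as written.
- **Intended distension.** The first symptom named is closely related to a state that the examination sets out to produce.

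Two results are at stake. The first is the plain safety rate, which is labelled as safety of MCCG and so reads as harm attributable to it. The second is the between-arm comparison. Background shared by both arms moves that comparison toward no difference, which for a tolerance question is the falsely reassuring direction.

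**Working it through.** **1. No safety figure to reproduce.** The documents give no adverse-event rate, background rate or power for safety. The only sample-size figure is for the primary outcome: 64 patients, raised for 20% withdrawal, 64 / (1 − 0.20) = 80, as stated. With 1:1 allocation that is 40 per arm, used below.

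**2. Water taken by the time the capsule is swallowed.** 100 + 200 + 800 + about 100 = about 1,200 ml in both arms, with more if distension is judged insufficient.

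**3. Effect of shared background.** Let r be the true new-onset rate in an arm. Let b be the share who would show a listed symptom anyway, equal in both arms and independent of true harm.

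- Observed rate = b + (1 − b)r
- Observed risk difference = (1 − b)(r₂ − r₁)

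Every arm's rate rises, and the difference shrinks by the factor (1 − b).

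**4. Illustration.** All values of b and r are assumptions. Power is for the uncorrected Pearson chi-square at two-sided 0.05, by exact binomial enumeration with 40 per arm.

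| Assumed r₁ v r₂ | b | Observed rates | Risk difference (points) | Risk ratio | Power |
|---|---|---|---|---|---|
| 5% v 25% | 0 | 5% v 25% | 20 | 5.0 | 76% |
| | 20% | 24% v 40% | 16 | 1.7 | 33% |
| | 30% | 33.5% v 47.5% | 14 | 1.4 | 25% |
| | 50% | 52.5% v 62.5% | 10 | 1.2 | 16% |
| 5% v 20% | 0 | 5% v 20% | 15 | 4.0 | 57% |
| | 20% | 24% v 36% | 12 | 1.5 | 21% |
| | 30% | 33.5% v 44% | 10.5 | 1.3 | 16% |
| | 50% | 52.5% v 60% | 7.5 | 1.1 | 11% |

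Example for b = 20%: 0.20 + 0.80 × 0.05 = 24%, and 0.20 + 0.80 × 0.25 = 40%. At 10% v 30% the pattern is the same: 63%, 32%, 26% and 15%.

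**5. What a baseline rule can and cannot remove.** A patient nauseated before dimethicone and unchanged later is removed by a new-or-worse rule. A patient who becomes distended after the water is new-onset and still counts. That part has to be shown separately.

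**6. Timing.** Position change takes place in a 15-minute period right after dimethicone. The 200 ml and 800 ml drinks follow at 30 and 40 minutes, and the examination comes after them. Symptoms that start and settle during position change fall outside the monitoring window, with or without a baseline reading.

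**The case against.** The best reply has five parts.

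- **The text permits the problem; it does not state it.** A reader might infer that presenting symptoms and intended distension are in fact scored as harms. The Protocol does not say so, and an assessor might have used judgement. This stands: the supportable statement is that the definition does not prevent it.
- **How common such symptoms are at entry is not documented.** The entry complaints are not itemised, obstruction symptoms are excluded, and a complaint that led to referral need not be present after an overnight fast. This stands, and it is why b can only be assumed.
- **The window limits what is recorded.** It does, but a symptom carried into the examination is still present in it, and observation that starts then cannot separate old from new.
- **Randomisation and equal planned water protect the comparison.** They protect it from favouring an arm. They do not prevent inflated rates or a smaller difference.
- **Safety is unpowered anyway.** This stands. Even with b = 0, power with 40 per arm is 57% for 5% v 20%, 35% for 5% v 15% and 15% for 5% v 10%. The definition is not the only limit, but it weakens an already imprecise comparison.

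A reader might also infer that poor tolerance of position change itself would be missed because there is no baseline. The documents do not support that in general: the window leaves out the position-change period, so only symptoms persisting into the examination are affected.

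**Conclusion.** The point holds as a limited weakness of a secondary outcome. As defined, the safety rate can mix presenting symptoms, the expected effect of the water and true harm, and the plan collects nothing that would separate them. The rate could be overstated in both arms. If background is equal across arms and independent of true harm, any arm difference shrinks by (1 − b).

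The size cannot be known from the documents. Under the assumed rates tried, a background of 20% cuts power by about half or more. On the absolute scale the change is milder: 20 points becomes 16.

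Two stronger conclusions are not supported. One is that the definition biases the result toward an arm. The other is that it touches the primary cleanliness score. This is an inexpensive improvement, not a flaw that threatens the trial's main conclusion.

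**What to change.** - **Baseline reading.** The study nurse records presence and severity (none, mild, moderate, severe) of distention, nausea, vomiting and abdominal pain once before dimethicone.
- **Definition.** In Secondary Outcome Measure, count as an adverse event only a symptom absent at that reading or worse than it was then.
- **Table.** Show distention after the water load on its own lines by severity, because the baseline rule does not remove it.
- **Scope.** State that inference on tolerance of position change is limited to symptoms persisting into the examination.
- **If no baseline was collected.** Report the figure as symptoms present during the procedure, not as harms of MCCG.

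Cost: about a minute per patient, one more form, one changed sentence and a few table lines. Preparation and care stay as they are.

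### The symptom-monitoring window is undefined and, on its natural reading, opens at least 25 minutes after the randomised position change has ended

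*Protocol*

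**What the plan says.** The Protocol, under Secondary Outcome Measure, lists safety of MCCG among the secondary outcomes. It gives distention, nausea and vomiting as examples of adverse events and says these "were monitored closely during the MCCG procedure". The only safety follow-up described beyond that is for capsule retention, up to two weeks.

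The section Gastric preparation regimen and MCCG examination protocol sets out the timeline. Right after dimethicone in 100 ml of water, one arm is told to "repeatedly change the body position according to a pre-specified protocol for a period of 15 min", while the other may walk about. After that the arms are treated alike: "Thirty and forty min after dimethicone administration, subjects in both groups would additionally take 200 ml and 800 ml water", "respectively before undergoing MCCG examination". The recorder is then fitted and the patient lies down. "Then the capsule was swallowed in a supine position with approximately 100 ml of water".

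The SAP gives a general rule that categorical variables are compared with a Chi-square test. It names no specific safety analysis.

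**The concern.** The randomised difference lies wholly in the preparation phase, but the stated symptom window is tied to MCCG. If that window begins with the capsule examination, the trial observes symptoms only after the period in which the arms differ. Discomfort that arises during the manoeuvre or the wait, and settles before the examination, would not be recorded.

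What is at stake is the meaning of a between-arm safety comparison. Events seen during the examination largely follow exposures that both arms share: most of the water and the same examination positions. Similar rates would then be weak evidence that the position change carries no tolerability cost, which matters to anyone deciding whether to adopt it. The primary outcome is not affected.

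**Working it through.** There is no stated figure to reproduce. The check is a timeline, with minute 0 at dimethicone ingestion. All times and volumes come from the Protocol section Gastric preparation regimen and MCCG examination protocol.

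**Inputs**
- Position change: starts right after dimethicone and lasts 15 minutes, so minutes 0 to 15.
- Shared drinks: 200 ml at minute 30 and 800 ml at minute 40, both before the examination.
- Capsule: swallowed after the recorder is fitted and the patient lies down, with about 100 ml of water. No clock time is given.

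**Which reading of the term.** The same section heading names preparation and examination as separate things, and the text puts the drinks before the examination. Both favour the narrow reading (the capsule examination only). Neither settles it, because the outcome section says procedure where the timeline says examination.

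**Overlap and gap**

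| Reading | Window opens | Overlap with the 15 minutes | Gap after the manoeuvre |
|---|---|---|---|
| Narrow: capsule examination | minute 40 or later | 0 of 15 | at least 40 - 15 = 25 min |
| Broad: preparation included | minute 0 | 15 of 15 | none |

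The 25 minutes is a minimum. Drinking 800 ml, fitting the recorder and positioning the patient take further time that is not stated.

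**Shared exposure.** Scheduled water before the manoeuvre: 100 ml. After it, in both arms: 200 + 800 + about 100 = about 1,100 ml. Share taken after the manoeuvre: 1,100 / 1,200 = about 92%, not counting any extra water given for distension. Distention or nausea seen during the examination may therefore reflect the water in either arm.

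**Missed events.** These are not computed. The documents give no symptom rate, so any number would be invented.

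**Precision of any added data** (this does not measure the problem itself). The SAP gives 80 / 2 = 40 patients per arm enrolled and 32 per arm required. With 0 events in an arm, the exact two-sided 95% upper limit is 1 - 0.025^(1/n): 8.8% for n = 40 and 10.9% for n = 32. Counts of this size support description, not a significance test.

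**The case against.** The strongest reply is that nothing here is an error. The outcome is named safety of MCCG and is monitored around MCCG, so the window fits its label. The plan sets out no tolerability outcome for the preparation, states no safety hypothesis, and nowhere says that similar event rates would clear the manoeuvre. This stands. The point is a limit on what is measured, and a reader who inferred a contradiction would be going beyond the text.

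Second, the gap depends on an undefined word. On the broad reading it vanishes, and the supplementary figure cited at the end of the preparation timeline, which might mark the window, is not shown. This also stands, and it makes every statement about the gap conditional. A reader might infer that tolerability of the position change was never assessed. The documents do not support that: they describe no symptom recording before the examination, but they do not exclude it either.

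Third, the practical effect may be small. The manoeuvre is brief, and the two positions listed for it, supine and left lateral, are also used in the examination in both arms. Symptoms lasting into the examination would still be seen. This is fair, and it is why the window says little about the manoeuvre rather than nothing.

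Fourth, the recruitment sentence in the opening part of the Protocol ("From May 7 to May 31 2018, consecutive patients") suggests that collection may be over, so new checks could come too late. That affects which remedy applies. The need to say which window was used remains.

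**Conclusion.** The concern holds in a conditional and minor form. The symptom window is undefined. On the natural reading it covers 0 of the 15 minutes in which the arms differ and opens at least 25 minutes after they end, so a between-arm comparison would say little about tolerability of the manoeuvre. On the broad reading there is no gap, and only the wording needs attention.

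The 25-minute figure rests on two assumptions: that the procedure means the capsule examination, and that the protocol's schedule is kept. The number of missed events, and any difference between arms in that number, is unknown and could be zero. It would be wrong to infer that harms were overlooked. The documents show only that, under one reading, brief symptoms in the preparation phase would not be recorded.

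**What to change.** **If recording can still be set.** Amend Secondary Outcome Measure along these lines: symptoms are recorded in both arms from dimethicone ingestion to the end of MCCG, with identical questions at the existing 30- and 40-minute contacts and during the examination; preparation-phase and MCCG-phase events are reported separately by arm as descriptive counts. Define the end of MCCG in the same sentence.

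**If data are already collected.** State which window was actually used. Only if preparation was not covered, confine the safety conclusion to the MCCG phase and say that tolerability of the position change during preparation was not assessed.

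**Cost.** For completed data, one or two sentences in the report. For prospective use, two short symptom checks per patient at contacts that already exist (a few minutes of nurse time, which is an assumption because the documents give no staffing figures) and an adverse-event table split into two phases. Reported event counts may rise.

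The reports would also not be blinded. Patients know what they did, and "subjects in the position change group were instructed by the study nurses". The blinding described covers the two image graders, of whom the Protocol says each "was blinded to the type of gastric preparation, independently graded the quality by reviewing the images captured by MCCG". Identical questions reduce this bias but do not remove it, and the report should say so.

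### Symptom collection is stated only for the procedure while capsule retention is followed for up to two weeks, so later symptoms that settle without intervention fall outside both safety measures

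*Protocol*

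**What the plan says.** The protocol, under Outcome parameters, Secondary Outcome Measure, lists the outcomes: "Secondary outcomes included detection rate of positive findings, number of lesions per patient (NLPP), gastric examination time, and safety of MCCG". It then treats safety in two parts, one directly after the other.

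- **Symptoms.** Adverse events are "defined as symptoms or signs such as abdominal distention, nausea, or vomiting", and these "were monitored closely during the MCCG procedure".
- **Retention.** Two conditions define it. One is that the capsule is still in the gut beyond two weeks. The other is the need for treatment, worded as "a capsule endoscope that requires directed intervention or therapy to aid its expulsion". Retention so defined "was monitored and followed up for up to two weeks".

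The SAP gives general tests for categorical and continuous variables. It has no adverse-event window and no analysis specific to safety.

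**The concern.** The two parts of the safety outcome have different windows. By following the capsule for up to two weeks, the protocol accepts that risk continues after the patient leaves the examination couch. The symptom part, however, has a stated window that closes with the procedure.

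The listed symptoms can plausibly start later. By the protocol's own schedule each patient drinks about 1.2 litres around the examination, and the capsule then has to travel through the rest of the gut. If symptoms from that period are not recorded, a low count describes the examination and cannot be read as the safety of MCCG over the period for which patients are followed. The outcome is named as safety of MCCG without qualification, so the label promises more than the stated collection delivers.

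**Working it through.** The plan states no figure on this point, so the check is mainly a comparison of the two rules.

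**Step 1. Other places where symptoms might be collected.** Neither document describes a telephone call, diary, visit or symptom question after the procedure. The only activity described beyond it is retention follow-up, and its form is not given.

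**Step 2. Apply both rules to possible events.**

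| Event | Symptom measure (procedure) | Retention measure (up to two weeks) |
|---|---|---|
| Distention during the examination | counted | not applicable |
| Vomiting after the procedure, settles unaided | outside stated window | does not meet definition |
| Pain and vomiting on day 4, capsule then passes unaided | outside stated window | does not meet definition |
| Capsule needs intervention on day 4 | accompanying symptoms outside stated window | counted |
| Capsule still present after two weeks | later symptoms, if any, outside stated window | counted |

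The gap is the second and third rows: symptoms that begin later and resolve without intervention.

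**Step 3. Does the result depend on what the procedure means?** The protocol does not define its end. On the widest reading, recording until the batteries run out (10 to 12 hours, Magnetically controlled capsule gastroscopy system), vomiting the same evening might be covered. Day 4 would still lie outside. The gap narrows under that reading but does not close.

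**Step 4. Fluid load.** From Gastric preparation regimen and MCCG examination protocol: 100 ml with dimethicone, then 200 ml and 800 ml, then about 100 ml with the capsule. 100 + 200 + 800 + 100 = about 1,200 ml. More water is allowed if distension is insufficient, so this is a minimum. It makes later symptoms plausible but does not show how often they occur.

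**Step 5. What a clean result could say.** The SAP requires 64 patients and allows 20% withdrawal: 64 / (1 − 0.20) = 80, or 80 / 2 = 40 per arm, which matches its stated enrolment. With zero events in n patients, the one-sided 95% upper limit is 1 − 0.05^(1/n).

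- n = 40: 1 − 0.05^(1/40) = 7.2%
- n = 80: 1 − 0.05^(1/80) = 3.7%

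For symptoms, these limits would apply to the procedure window only. Zero events is an illustration, not a reported result.

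**Related wording.** Retention is partly defined as presence beyond two weeks, while follow-up runs up to two weeks. That condition can be judged only at the very end of follow-up or after it, so the two phrases must be reconciled.

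**The case against.** **Silence is not exclusion.** The protocol does not say that later symptoms were disregarded. A reader might infer that they were never counted, or that nobody was responsible for asking. The documents do not support either inference: they state one window and are silent beyond it. Learning whether a capsule needed intervention also means learning something of what happened to the patient. Supplementary Figure S1 and the consent material are not available here, so any instructions to patients in them cannot be checked. This objection stands against the stronger reading. It does not supply a provision for recording later symptoms.

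**The follow-up may not be a conversation.** Its form is undescribed, so one cannot be sure that a question can simply be added to an existing contact. This stands, and the cost below is stated accordingly.

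**Comparing clock times.** A reader might set the length of the procedure against two weeks and conclude that almost all safety information is lost. The protocol gives no procedure length, two weeks is a maximum, and exposure to dimethicone, water and capsule manipulation is concentrated before and during the examination. A ratio of minutes does not measure missed events, and none is used here.

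**Relevance to the randomised contrast.** Both arms receive the same dimethicone, water and capsule. They differ only in the activity after dimethicone: 15 minutes of position change or free walking. Symptoms on day 4 say little about that contrast. This is a fair point, but the outcome is worded as safety of MCCG, which both arms undergo, and not as safety of position change.

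**Noise.** Patients enter with upper abdominal complaints, so later questions will pick up some of the presenting complaint. This stands, and it is why the fix needs a record before preparation.

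**Held-up capsules.** A reader might infer that these go undetected. They do not: a capsule that needs intervention meets the retention definition.

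**Conclusion.** The concern holds in a limited form. The stated symptom window ends with the procedure, and neither document provides for symptoms that begin later. Those that resolve without intervention therefore fall outside both safety measures. The safety result supports a statement about symptoms during the procedure and about retention, and no broader statement about the safety of MCCG.

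The number of events missed cannot be estimated, because the documents give no rate of later symptoms. The conclusion rests on taking the stated window at its word and on finding no other provision in the two documents. It does not depend on an assumed procedure length.

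The GCS comparison, its sample size and its test are untouched. This is something the sponsor should correct because it limits a secondary outcome; it does not threaten the trial's main result.

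**What to change.** **If symptoms can still be collected**

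1. At the existing retention follow-up, also record abdominal pain, distention, nausea, vomiting and any unplanned visit since the examination. For each, note the onset date, whether the capsule had passed, and whether EGD was done. EGD status matters because patients with lesions go on to that procedure, which may cause symptoms of its own.
2. Record the same symptoms before preparation, so that new or worse symptoms can be told from the presenting complaint.
3. Describe how the follow-up is carried out, and state when the procedure ends.
4. In the SAP, tabulate procedural and later events separately by arm.

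**If collection is already complete**, label the outcome as symptoms during the procedure and limit safety conclusions to match.

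**Cost.** The full change needs a short symptom record before preparation, a few questions at follow-up, a sentence or two in Secondary Outcome Measure and one table in the SAP. If the follow-up does not at present involve speaking to the patient, a contact has to be added, which costs more. Later symptoms would be patient-reported, and some would still reflect the presenting complaint, so they should not be pooled with events observed during the procedure. The relabelling alone costs one sentence.
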